## **9.1. Efficacy**

This study is a single dose PK study and therefore there is no efficacy endpoint.

## **9.2. Adverse Events**

The definitions of an AE or SAE can be found in [Appendix 4](#).

The investigator and any designees are responsible for detecting, documenting, and reporting events that meet the definition of an AE or SAE and remain responsible for following up AEs that are serious, considered related to the study treatment or the study, or that caused the participant to discontinue the study (see [Appendix 4](#)).

### **9.2.1. Time Period and Frequency for Collecting AE and SAE Information**

- All SAEs will be collected from the signing of the ICF until the follow-up visit at the time points specified in the SoA ([Section 2](#)).
- All AEs will be collected from the start of treatment until the follow-up visit at the time points specified in the SoA ([Section 2](#)).

- Medical occurrences that begin before the start of study treatment but after obtaining informed consent will be recorded on the Medical History/Current Medical Conditions section of the case report form (CRF) not the AE section.
- All SAEs will be recorded and reported to the sponsor or designee within 24 hours, as indicated in [Appendix 4](#). The investigator will submit any updated SAE data to the sponsor within 24 hours of it being available.
- Investigators are not obligated to actively seek AEs or SAEs in former study participants. However, if the investigator learns of any SAE, including a death, at any time after a participant has been discharged from the study, and he/she considers the event to be reasonably related to the study treatment or study participation, the investigator must promptly notify the sponsor.
- The method of recording, evaluating, and assessing causality of AEs and SAEs and the procedures for completing and transmitting SAE reports are provided in [Appendix 4](#).

#### **9.2.2. Method of Detecting AEs and SAEs**

Care will be taken not to introduce bias when detecting AE and/or SAE. Open-ended and non-leading verbal questioning of the participant is the preferred method to inquire about AE occurrence.

#### **9.2.3. Follow-up of AEs and SAEs**

After the initial AE/SAE report, the investigator is required to proactively follow each participant at subsequent visits/contacts. All SAEs will be followed until the event is resolved, stabilized, otherwise explained, or the participant is lost to follow-up (as defined in Section 8.3). Further information on follow-up procedures is given in [Appendix 4](#).

#### **9.2.4. Regulatory Reporting Requirements for SAEs**

- Prompt notification by the investigator to the sponsor of a SAE is essential so that legal obligations and ethical responsibilities towards the safety of participants and the safety of a study treatment under clinical investigation are met.
- The sponsor has a legal responsibility to notify both the local regulatory authority and other regulatory agencies about the safety of a study treatment under clinical investigation. The sponsor will comply with country-specific regulatory requirements relating to safety reporting to the regulatory authority, Institutional Review Boards (IRB)/Independent Ethics Committees (IEC), and investigators.
- Investigator safety reports must be prepared for suspected unexpected serious adverse reactions (SUSAR) according to local regulatory requirements and sponsor policy and forwarded to investigators as necessary.

- An investigator who receives an investigator safety report describing a SAE or other specific safety information eg, summary or listing of SAE) from the sponsor will review and then file it along with the Investigator's Brochure and will notify the IRB/IEC, if appropriate according to local requirements.

### **9.2.5. Pregnancy**

- Details of all pregnancies in female participants will be collected after the start of study treatment and until 60 hours after the last dose of study treatment.
- If a pregnancy is reported, the investigator should inform GSK within 24 hours of learning of the pregnancy and should follow the procedures outlined in [Appendix 5](#).
- Abnormal pregnancy outcomes (eg, spontaneous abortion, fetal death, stillbirth, congenital anomalies, ectopic pregnancy) are considered SAEs.

### **9.3. Treatment of Overdose**

For this study, any dose of study treatment  $\geq$  4 tablets in a day will be considered an overdose.

GSK does not recommend specific treatment for an overdose.

In the event of an overdose, the investigator/treating physician should:

1. Contact the Medical Monitor immediately.
2. Closely monitor the participant for AE/SAE and laboratory abnormalities until danirixin can no longer be detected systemically (at least 3 days).
3. Obtain a sample for PK analysis within 4 days from the date of the last dose of study treatment if requested by the Medical Monitor (determined on a case-by-case basis).
4. Document the quantity of the excess dose as well as the duration of the overdosing in the CRF.

Decisions regarding dose interruptions or modifications will be made by the investigator in consultation with the Medical Monitor based on the clinical evaluation of the participant.

### **9.4. Safety Assessments**

Planned time points for all safety assessments are provided in the [Section 2](#).

#### **9.4.1. Physical Examinations**

- A complete physical examination will include, at a minimum, assessments of the Cardiovascular, Respiratory, Gastrointestinal and Neurological systems. Height and weight will also be measured and recorded.

- A brief physical examination will include, at a minimum, assessments of the skin, lungs, cardiovascular system, and abdomen (auscultation and palpation of the abdomen including examination of the liver and spleen).
- Investigators should pay special attention to clinical signs related to previous serious illnesses.

#### **9.4.2. Vital Signs**

- Oral temperature, pulse rate, respiratory rate, and blood pressure will be assessed. Heart Rate and Blood Pressure will be assessed at 24 and 48 hours post dose and at the early termination/final follow-up visit only.
- Blood pressure and pulse measurements will be assessed with a completely automated device. Manual techniques will be used only if an automated device is not available.
- Blood pressure and pulse measurements should be preceded by at least 5 minutes of rest for the participant in a quiet setting without distractions (eg, television, cell phones).
- Vital signs (to be taken before blood collection for laboratory tests) will consist of 1 pulse and 3 blood pressure measurements (3 consecutive blood pressure readings will be recorded at intervals of at least 1 minute) at time points specified in Section 2. The average of the 3 blood pressure readings will be recorded on the CRF.
- Vital signs will be measured in a semi-supine position after 5 minutes rest and will include temperature, systolic and diastolic blood pressure, and pulse and respiratory rate.

#### **9.4.3. Electrocardiograms**

- Single 12-lead ECG will be obtained as outlined in the SoA (Section 2) using an ECG machine that automatically calculates the heart rate and measures PR, QRS, QT, and QTc intervals. Refer to Section [8.1.2] for QTc withdrawal criteria and additional QTc readings that may be necessary.

#### **9.4.4. Clinical Safety Laboratory Assessments**

- Refer to [Appendix 2](#) for the list of clinical laboratory tests to be performed and to the SoA for the timing and frequency.
- The investigator must review the laboratory report, document this review, and record any clinically relevant changes occurring during the study in the AE section of the CRF. The laboratory reports must be filed with the source documents. Clinically significant abnormal laboratory findings are those which are not associated with the underlying disease, unless judged by the investigator to be more severe than expected for the participant's condition.
- All laboratory tests with values considered clinically significantly abnormal during participation in the study or within 3 days after the last dose of study

treatment should be repeated until the values return to normal or baseline or are no longer considered significantly abnormal by the investigator or medical monitor.

- If such values do not return to normal/baseline within a period of time judged reasonable by the investigator, the etiology should be identified and the sponsor notified.
- All protocol-required laboratory assessments, as defined in [Appendix 2](#), must be conducted in accordance with the laboratory manual and the [Section 2](#).
- If laboratory values from non-protocol specified laboratory assessments performed at the institution's local laboratory require a change in participant management or are considered clinically significant by the investigator (eg, SAE or AE or dose modification), then the results must be recorded in the CRF.

## **9.5. Pharmacokinetics**

- Whole blood samples of approximately 2 mL will be collected for measurement of whole blood concentrations of danirixin (performed under the control of GSK Platform Technology and Science Department of In Vitro In Vivo Translation Third Party Resourcing (PTS-IVIVT/TPR) as specified in the [Section 2](#). Instructions for the collection and handling of biological samples will be provided by the sponsor in the SRM. The actual date and time (24-hour clock time) of each sample will be recorded.
- Samples will be used to evaluate the PK of danirixin. Each whole blood sample will be used to prepare 4 dried blood spots which will be analysed for danirixin concentrations. Samples collected for analyses of danirixin whole blood may also be used to evaluate safety or efficacy aspects related to concerns arising during or after the study.

## **9.6. Pharmacodynamics**

Pharmacodynamic parameters are not evaluated in this study.

## **9.7. Genetics**

Genetics are not evaluated in this study.

## **9.8. Biomarkers**

Biomarkers are not evaluated in this study.

# **10. STATISTICAL CONSIDERATIONS**

No formal hypothesis will be tested. For each pharmacokinetic endpoint, point estimates and corresponding 90% confidence intervals will be constructed for the ratio of the geometric mean of the test treatment to the geometric mean of the reference treatment,  $\mu(\text{test})/\mu(\text{reference})$ .

The following comparisons of interest will be constructed:

Part	Question	Comparison
Part A Group 1	Formulation fed	475mg DC tablet formulation versus 600mg RC formulation (reference)
		600mg DC tablet formulation versus reference
		600mg DC tablet with 5% HPMC versus reference
Part A Group 2	Formulation fasted	475mg DC tablet formulation versus 600mg RC formulation (reference)
		600mg DC tablet formulation versus reference
		600mg DC tablet with 5% HPMC versus reference
Part A Group 1 & 2	Food effect	600mg RC formulation fed versus fasted
		475mg DC tablet formulation fed versus fasted
		600mg DC tablet formulation fed versus fasted
		600mg DC tablet with 5% HPMC fed versus fasted
Part B Group 1	Food effect No OMP	High fat meal (heavy) versus Fasted
		Normal meal (light) versus Fasted
		High fat meal (heavy) versus Normal meal (light)
Part B Group 2	Food effect With OMP	High fat meal (heavy) versus Fasted
		Normal meal (light) versus Fasted
		High fat meal (heavy) versus Normal meal (light)
Part B Group 1 & 2	Drug interaction	Fasted with OMP versus Fasted without OMP
		Normal meal (light) with OMP versus Normal meal (light) without OMP
		High fat meal (heavy) with OMP versus High fat meal (heavy) without OMP
Part B Group 1	Pharm Dev	Monohydrate with high fat meal versus High fat meal (heavy)

### 10.1. Sample Size Determination

The sample size is primarily based on feasibility. Approximately 60 participants will be enrolled in the study to obtain approximately 8 randomized participants (6 completers) in each group in Part A and approximately 12 randomized subjects (10 completers) in each group in Part B.

[figure not shown]
The within-subject variability for AUC(0-inf), AUC(0-t) and Cmax of danirixin [GSK Study 201037, GlaxoSmithKline Document Number [2015N248339\\_00](#)] was estimated to be 37.3%, 39.3% and 44.7%, respectively. Based upon the largest within-subject coefficient of variation (44.7% for Cmax of danirixin) and a sample size of 6 subjects completing each group in part A of the study, it is estimated that the half-width of the 90% confidence interval for the ratio of geometric means for the comparison of interest should be no more than 42% of the point estimates. Assuming an observed ratio of one, the corresponding 90% confidence interval for the ratio of geometric means would be 0.70 to 1.42.

A PK interim analysis is planned at the completion of Part A to select the formulation for evaluation in Part B.

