#### 10.3.1. Pharmacokinetic Analyses

Pharmacokinetic parameters will be calculated by standard non-compartmental analysis according to GlaxoSmithKline current working practices. Calculations will be based on the actual sampling times recorded during the study. From the blood concentration-time data, the following pharmacokinetic parameters will be determined, as data permit: maximum observed blood concentration (Cmax), time to Cmax (tmax), area under the blood concentration-time curve [AUC(0-t), AUC(0-inf), AUC(0-24)], lag time before observation of first blood concentration (tlag), time of last observed blood concentration (tlast), and apparent terminal phase half-life (t1/2).

Pharmacokinetic data will be listed and presented in graphical form and will be summarized descriptively. Complete details will be documented in the Reporting and Analysis Plan (RAP).

The point estimates of the geometric least squares (GLS) mean ratio for the PK parameters (AUC and Cmax) and the associated 90% CIs will be provided for treatment comparisons (test:reference). The PK parameters will be log-transformed prior to analysis and treatment comparisons will be expressed as ratios on the original scale.

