## 10.1. Sample Size Determination

The sample size is primarily based on feasibility. Approximately 60 subjects will be enrolled in the study to obtain approximately 16 randomized subjects (13 completers) in Part A and 12 randomized subjects (10 completers) in each strata of Part B.

[figure not shown]
The within-subject variability for AUC(0-inf), AUC(0-t) and Cmax of danirixin [GSK Study 201037, GlaxoSmithKline Document Number [2015N248339\\_00](#)] was estimated to be 37.3%, 39.3% and 44.7%, respectively. Based upon the largest within-subject coefficient of variation (44.7% for Cmax of danirixin) and a sample size of 13 subjects completing part A of the study, it is estimated that the half-width of the 90% confidence interval for the ratio of geometric means for the comparison of interest should be no more than 23% of the point estimates. Assuming an observed ratio of one, the corresponding 90% confidence interval for the ratio of geometric means would be 0.81 to 1.23.

An interim analysis is planned at the completion of Part A to select the formulation for evaluation in Part B.

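### The Part A precision in Protocol Section 10.1 (half-width 42%, 90% CI 0.70 to 1.42) omits the factor √2 for a difference between two treatments; with 6 completers and a CV of 44.7% it should be about 52%.

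*Protocol*

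**What the plan says.** Protocol Section 10 tests no hypothesis. It plans estimation: "point estimates and corresponding 90% confidence intervals will be constructed for the ratio of the geometric mean of the test treatment" over that of the reference. Section 10.3.1 fixes the scale: "The PK parameters will be log-transformed prior to analysis and treatment comparisons will be expressed as ratios on the original scale".

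Section 10.1 says the sample size is mainly a matter of feasibility, then states the expected precision for Part A. It takes the largest of three within-subject CVs from an earlier danirixin study (37.3% for AUC(0-inf), 39.3% for AUC(0-t), 44.7% for Cmax) and "a sample size of 6 subjects completing each group in part A of the study". From these it concludes that the half-width "for the comparison of interest should be no more than 42% of the point estimates", and that at an observed ratio of one "the corresponding 90% confidence interval for the ratio of geometric means would be 0.70 to 1.42".

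SAP Section 7.1.5.1 specifies the model: all Part A data together, period and treatment as fixed effects, participant as random, and the 90% CI for each difference in least squares means built from the residual variance. SAP Section 10.5.3 defines the within-participant CV as √(exp(MSE) − 1), with MSE from that model.

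**The concern.** The interval is described as one for a ratio of two treatment geometric means. On the log scale that is a difference of two means, each with its own sampling error, so the within-subject variance enters twice. The stated limits look too narrow for that.

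Section 10.1 gives the only numerical precision in the protocol text, and it concerns the part of the study whose interim PK analysis selects the Part B formulation. A team relying on it would expect Part A to resolve formulation differences more finely than the design allows. The comparison table in Section 10 also lists four Part A fed-versus-fasted comparisons. Groups 1 and 2 are different people, so a half-width built from within-subject variance alone cannot apply to those, and no other precision is given for them in the text.

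**Working it through.** **Inputs.** CV 44.7%, 6 completers per group, 90% two-sided interval, observed ratio 1 (Protocol Sections 10 and 10.1). Four periods per participant in Part A (Protocol Section 5.1). Model from SAP Section 7.1.5.1.

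**Log-scale within-subject SD.** σ = √ln(1 + 0.447²) = 0.4268.

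**The protocol's own figure.** Limits exp(±t(0.95, n−1) × σ/√n), the interval for one mean:

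- n = 6, 5 df: 2.0150 × 0.4268/√6 = 2.0150 × 0.1742 = 0.3511, giving 0.704 to 1.421, half-width 42.06%. This matches the stated 0.70 to 1.42 and 42%.
- n = 13, 12 df: 1.7823 × 0.4268/√13 = 0.2110, giving 0.810 to 1.235, half-width 23.5%. The superseded original protocol planned 13 completers in Part A and stated that "the corresponding 90% confidence interval for the ratio of geometric means would be 0.81 to 1.23". That text is cited only because it shows the same formula at work.

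Other variants for n = 6 without √2 do not match: 12 df gives 36.4%, the normal quantile 33.2%, and the raw CV used as the SD (5 df) 44.4%.

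**Corrected formula.** The test-minus-reference difference has SE = σ × √(2/n) = 0.4268 × √(2/6) = 0.2464, with limits exp(±t × SE).

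Within-subject degrees of freedom with 6 completers per group:

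- Joint Part A model: 48 observations − 12 participants − 3 periods − 6 within-group treatment contrasts = 27.
- One group alone: 24 − 6 − 3 − 3 = 12.

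| Completers per group | Analysis | df | Half-width | 90% CI |
|---|---|---|---|---|
| 6 | Joint Part A model (SAP) | 27 | 52% | 0.66 to 1.52 |
| 6 | One group alone | 12 | 55% | 0.64 to 1.55 |
| 6 | Paired t | 5 | 64% | 0.61 to 1.64 |
| 6 | Normal quantile (lower bound) | – | 50% | 0.67 to 1.50 |
| 8 | Joint Part A model | 39 | 43% | 0.70 to 1.43 |
| 9 | Joint Part A model | 45 | 40% | 0.71 to 1.40 |

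Under the joint model, 42% is first met at 9 completers per group, one more than the 8 randomised. With the correct SE, limits of ±ln 1.42 carry about 82% (12 df) to 83% (27 df) confidence, not 90%.

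**Smaller planning CVs.** With 6 completers and 27 df, 37.3% gives 42.6% and 39.3% gives 45.2%. The CV at which the half-width would equal 42% is about 37% (27 df) or 35% (12 df).

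**Fed versus fasted.** These contrasts also carry between-subject variance, for which the documents give no figure. Assume a between-subject CV of 30% to 50%, 6 participants per group and 10 df, with SE = √(2(σ_b² + σ²)/6), where σ_b² is the between-subject log variance and σ² = 0.1822:

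- CV 30%: σ_b² = ln 1.09 = 0.0862, SE = 0.299, CI 0.58 to 1.72.
- CV 50%: σ_b² = ln 1.25 = 0.2231, SE = 0.368, CI 0.51 to 1.95.

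**The case against.** The strongest reply concerns consequence. The size is set by feasibility, no hypothesis is tested, and no power, margin or acceptance limit depends on the 42%. The reported intervals will have the right width, because the SAP builds them from the residual variance of the fitted difference. Formulation selection rests on PK profile, relative bioavailability and between-participant variability, not on a planned half-width. All of this stands. The error misstates what Part A was expected to show; it does not alter what Part A can show, and it does not invalidate the sample size.

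Several narrower points also stand in part:

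- The shortfall is conditional on the planning CV. An observed CV of about 37% or less would give 42% under the joint model, and at the AUC(0-inf) value of 37.3% the corrected half-width is only just above it. However, the protocol makes its claim for the largest CV, and none of its three CVs meets 42% with 6 completers under the joint model.
- The SAP keeps the earlier periods of participants who withdraw. If two of the eight in each group left after two of the four periods, the half-width would be about 47% to 51%. That is better than 52% but still above 42%.
- Six completers cannot be balanced over four sequences, so period adjustment moves 52% to between 52% and 54%.
- Section 10.1.1 refers to a figure of half-widths by CV and sample size. It is not visible in the text available, so whether it repeats the error is unknown.
- If 44.7% were the CV of a paired difference, the stated interval would be right. The protocol calls it the within-subject coefficient of variation, and the SAP ties that term to the model MSE, a per-observation variance. That the earlier study used the same definition is an inference.

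**Conclusion.** The statement is wrong as written. The exact match at n = 6, and again at n = 13 in the superseded text, shows that the factor √2 was left out. For within-group formulation comparisons at a CV of 44.7% with 6 completers per group, the half-width is about 52%, roughly ten percentage points more than stated. No standard choice of degrees of freedom brings it below 50%. This rests on reading 44.7% as a per-observation within-subject CV and, for the 52%, on the SAP's joint model with approximately balanced sequences.

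The 42% does not cover the Part A food comparisons at all. Those intervals will be wider still, but by how much depends on a between-subject CV that the documents do not give. The consequence is limited to the precision that the plan advertises.

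**What to change.** In Protocol Section 10.1, restate the precision: with 6 completers per group and a within-subject CV of 44.7%, the half-width for within-group formulation comparisons is about 52% of the point estimate (90% CI 0.66 to 1.52 at a ratio of one), under the joint Part A model. Say that this does not apply to the fed-versus-fasted comparisons between groups, and give a separate figure for those using a stated between-subject CV. Check Figure 1 in Section 10.1.1 and redraw it if it used the same formula.

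The cost is a corrected sentence, one added figure for the food comparisons and possibly a redrawn plot. Enrolment and the SAP analysis stay as they are. The stated precision becomes less favourable.

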### 10.1.1. Sample Size Sensitivity

The figure below shows the half width of the 90% CI for a range of within-subject coefficient of variations for various sample sizes.

**Figure 1 Plot of half width of 90% CI by within-subject coefficient of variations**

### 10.1.2. Sample Size Re-estimation or Adjustment

No sample size re-estimation will be performed.

## 10.2. Populations for Analyses

For purposes of analysis, the following populations are defined:

Population	Description
All Participants	All participants who receive at least one dose of study medication. This population will be used for the study population and safety analyses.
PK	All participants for whom a pharmacokinetic sample was obtained and analyzed. This will be the population used for all the pharmacokinetic displays.

